### **9.2.3 EXPLORATORY ENDPOINT OF pk**

- Sarilumab  $C_{\text{trough}}$  at Day 1 and Day 85

### **9.2.4 PHARMACOKINETICS AND IMMUNOGENICITY**

#### **9.2.4.1 Sampling time**

Pre-dose serum samples will be collected for determination of serum concentration of sarilumab and ADA at Visit V101 (D1) and at Visit V102 (D85). See study flow chart ([Section 1.2](#)).

Serum trough concentrations of functional sarilumab will be evaluated in patients on stable dose of sarilumab at V101 (D1) before using the PFS-S and at Visit V102 (D85) after 12 weeks administration of sarilumab using the PFS-S in the sub-study. Patients are considered to be on stable dose of sarilumab at V101 (D1) if they received the same dose of sarilumab without treatment interruption for at least 24 weeks in LTS11210 prior to V101.

#### **9.2.4.2 *Sample handling procedure***

Sample handling procedures and bioanalytical method are same as in main study.

## 10 STUDY PROCEDURES

### 10.1 VISIT SCHEDULE

All the procedures performed in the sub-study are in addition to those planned in the main study unless sub-study procedures replace the main study procedures.

#### 10.1.1 Visit 101: Entry of sub-study / Day 1

A sub-study specific written informed consent form must be signed by the patient prior to any sub-study procedure being performed.

The following items will be checked and recorded by the Investigator or designee:

- Assess eligibility by review of inclusion criteria.
- Before sarilumab administration, obtain blood sample for PK (serum sarilumab) and anti-sarilumab antibodies assessment. If the sub-study visit coincides with a PK and ADA sampling time point in the main study, no samples are required to be obtained for the sub-study.
- Access IVRS/IWRS to enroll patient into the sub-study and to allocate sub-study IMP. NOTE: this replaces the scheduled resupply IVRS/IWRS transaction for the main scheduled study visit.
- Dispense sarilumab PFS-S.
- Dispense sub-study injection diary, provide instructions for use, and remind the patient to complete the diary after each injection and to bring the completed diary back to the site at next visit.
- Provide training on injection using a patient user instruction specific to the use of the PFS-S and a PFS-S prefilled with sucrose together with a pad. Allow the patient or the caregiver to inject into the training pad under observation, provide feedback on technique. This training must be documented in the patient's study file.
- The first dose of IMP will be administered by the patient or caregiver or study doctor/nurse at the study site and an appropriate record will be made in the source data by the person who performed the injection using the injection diary.

#### 10.1.2 Visit 102: End of sub-study / Day 85

- Check compliance to the IMP and collect PFS-S medication kits and syringes (used and unused).
- Collect injection diary and review for content and completeness.
- Report diary feedback on each injection into the e-CRF.
- Collect and assess any PTC using the injection diary. The Investigator will ask the patient whether there were any problems associated with the PFS-S – either during drug administration or otherwise and will obtain more details as appropriate.

- Inquire about and record any adverse events/SAEs related to PTC.
- Prior to the IMP administration (sarilumab in PFS), obtain blood sample for sub-study PK (serum sarilumab) and anti-sarilumab antibodies assessment. If the sub-study visit coincides with a PK and ADA sampling time point in the main study, no samples are required to be obtained for the sub-study.
- Access IVRS/IWRS to register the end of sub-study and to obtain the next scheduled IMP (sarilumab in PFS) if the patient returns to the main study.

## **10.2 DEFINITION OF SOURCE DATA**

Besides source data defined in the main study, the injection diary in sub-study is also considered as source data.

## **10.3 HANDLING OF PATIENT TEMPORARY OR PERMANENT TREATMENT DISCONTINUATION DURING THE SUB-STUDY AND OF PATIENT STUDY DISCONTINUATION**

Please refer to the main study as regards handling of patients at the time of temporary or permanent treatment discontinuation.

If the patient chooses to end the participation in the sub-study but to continue in the main study they should complete the Visit V102.

If a patient discontinues the Investigational Medicinal Product (IMP) permanently in LTS11210 during the sub-study, he/she should complete all procedures planned for V102 in the sub-study as well as the end of treatment (EOT) and post treatment follow-up visits in the main study (see flowchart in main study [Section 1.2](#)).

## **10.4 OBLIGATION OF THE INVESTIGATOR REGARDING SAFETY REPORTING**

### **10.4.1 Instructions for reporting PTC and adverse events related to PTC**

PTCs may or may not be associated with an adverse event. Any PTC of the PFS-S, whether or not associated with an adverse event, must be reported to the sponsor on a PTC form.

If a PTC is suspected of being associated with the occurrence of an adverse event, the Investigator must document the adverse event on an adverse event page in the e-CRF, in addition to completing the PTC form. The potential link of the adverse event with the PTC must be specified in AE verbatim.

If a PTC is suspected of being associated with the occurrence of an SAE, the SAE must be reported in accordance with the SAE reporting procedures and the Investigator must specify the potential link with the PTC in SAE verbatim.

Please refer to the related section in the main study for general safety instructions.

## **11 STATISTICAL CONSIDERATIONS**

### **11.1 DETERMINATION OF SAMPLE SIZE**

The sample size of this sub-study is based on empirical consideration. No formal sample size calculation is performed but an estimate of 120 patients included in this sub-study with up to 6 injections per patient will provide approximately 680 injections to evaluate PTF during the 12 weeks of the study assuming 5% of drop-out rate.

### **11.2 DISPOSITION OF PATIENTS**

Enrolled patients are defined as any patient who met the inclusion criteria and none of the exclusion criteria, and signed the informed consent.

### **11.3 ANALYSIS POPULATIONS**

The safety population will consist of all enrolled patients who receive at least 1 dose or part of a dose of IMP administered via PFS-S during this sub-study.

Safety analyses will be performed on the safety population. Patient data will be analyzed according to the treatment actually received (200mg q2w PFS-S, 150mg q2w PFS-S, dose reduction).

The PK population will consist of all enrolled patients who receive at least 1 dose of the IMP and at least one non-missing serum concentration value.

### **11.4 STATISTICAL METHODS**

The phrase ‘treatment group’ used throughout this section refers to the following device/dose groups (200mg q2w PFS-S, 150mg q2w PFS-S, 200mg q2w PFS-S to 150mg q2w PFS-S). The baseline value is defined as original baseline in initial studies.

#### **11.4.1 Extent of study treatment exposure and compliance**

The extent of study treatment exposure and compliance will be assessed and summarized by actual treatment received within the safety population.

The duration of IMP exposure is defined as: last dose date – first dose date at D1 + 14 days (regardless of unplanned intermittent discontinuations). The duration of exposure to the IMP will be summarized for each treatment group by using descriptive statistics such as mean, SD, median, minimum, and maximum.

Treatment compliance to the IMP is defined as the actual number of doses received compared to the scheduled number of doses during the treatment period. It is calculated according to the following formula:

$$\frac{100 \times \text{total number of doses administered}}{\text{nominal number of doses for the duration of exposure}}$$

A given administration will be considered noncompliant if the patient does not take the planned dose as required by the protocol. No imputation will be made for patients with missing or incomplete data.

Treatment compliance during the treatment period will be summarized descriptively (N, mean, standard deviation, median, minimum, and maximum). The percentage of patients with compliance <80% will be summarized.

#### **11.4.2 Analyses of endpoints**

##### **11.4.2.1 Analysis of primary endpoint(s)**

Data will be described for the 12 weeks of this sub-study using the safety population. The primary analysis variable is the number of validated PFS-S-associated PTFs during the sub-study. The primary analysis will be performed using descriptive statistics.

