## **4.2 SUB-STUDY RATIONALE**

This sub-study is aimed to assess the usability of the PFS-S syringe when used by patients with moderate or severe RA, or their professional or non-professional healthcare providers in an unsupervised real-world situation. To mimic the real-world practice, the sub-study was designed to incorporate into the LTS11210 study without additional visits compare to scheduled visits in the main study.

The primary endpoint is the number of product technical failures (PTF), which is defined as any product technical complaint (PTC) that has a validated technical cause. A PTC is defined as any patient- or healthcare provider-reported complaint regarding the use of the PFS-S syringe and collected via the completion of the injection diary.

In addition, the safety information of sarilumab 150 mg q2w PFS-S and 200 mg q2w PFS-S will be collected throughout the sub-study period and trough concentrations of sarilumab will be measured at entry into the sub-study and at the end of the 12-week sub-study period.

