## **Efficacy (Device) analysis**

Data will be described for the 12 weeks of this sub-study using the safety population. The efficacy analyses will be performed using descriptive statistics and presented by treatment group.

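### The PFS-S sub-study's primary result is a count of device failures with no injection denominator or interval, so it cannot express or bound the failure rate

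*Protocol*

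**What the plan says.** **Endpoint and analysis.** Protocol Appendix R 11.4.2.1 states: "The primary analysis variable is the number of validated PFS-S-associated PTFs during the sub-study". It adds: "The primary analysis will be performed using descriptive statistics". SAP Appendix K, under Efficacy (Device) analysis, says: "The efficacy analyses will be performed using descriptive statistics and presented by treatment group". Three groups are defined: 200 mg, 150 mg, and patients reduced from 200 mg to 150 mg during the sub-study.

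**Definition of a failure.** Under Appendix R 9.1, a product technical failure (PTF) is a complaint (PTC) for which the sponsor validates a technical cause. If that is ruled out, the event becomes a failed drug delivery (FDD). The numbers and percentages of patients with PTFs, PTCs and FDDs are secondary endpoints (Appendix R 9.2.1).

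**Planning basis.** Appendix R 11.1 says that "an estimate of 120 patients included in this sub-study with up to 6 injections per patient will provide approximately 680 injections", "assuming 5% of drop-out rate". It states that no formal sample size calculation was made.

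**Setting.** The rationale (Appendix R 4.2) concerns use "in an unsupervised real-world situation", by patients or by professional or non-professional carers. The formal objective (Appendix R 5.1) speaks only of usability. For Visit 101, Appendix R 10.1.1 says: "The first dose of IMP will be administered by the patient or caregiver or study doctor/nurse at the study site". That dose is entered in the same injection diary as the later ones.

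**The concern.** A failure count has meaning only against the number of attempts. The plan recognises this when it sizes the sub-study in injections, but the denominator is not carried into the primary analysis. Neither document specifies PTFs per injection or an interval for the primary variable. The only percentage planned for PTFs is of patients, and it is secondary.

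Two things are lost. First, the sub-study cannot state how high a failure rate its data leave open. That is the main thing a sample of this kind can offer when failures are few or absent. Second, results are laid out by three dose groups whose sizes follow from each patient's existing dose and any dose reduction. Equal counts in groups of unequal size do not mean equal performance.

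A smaller matter goes with this. The first of the six PFS-S injections takes place at the site on the day of training, and the later five normally take place elsewhere. The plan does not show the two settings separately.

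**Working it through.** **Inputs.** 120 patients, up to 6 injections each and 5% drop-out (Appendix R 11.1); 6 PFS-S injections over 12 weeks (Appendix R 8.1); first dose on site (Appendix R 10.1.1). The Day 85 dose uses the ordinary PFS (Appendix R 10.1.2), so it is not one of the six.

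**Step 1: the plan's own figure.** 120 × 0.95 × 6 = 684, against the stated figure of about 680. It reproduces. If the six drop-outs instead left after their first dose, the total would be 120 + 114 × 5 = 690, also consistent.

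**Step 2: first and later doses.** First doses: 120 × 0.95 × 1 = 114, or 114/684 = 16.7%. In the drop-out variant, 120/690 = 17.4%. Later doses: 120 × 0.95 × 5 = 570.

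**Step 3: what a rate with an interval would show.** Exact (Clopper-Pearson) two-sided 95% limits per injection, treating injections as independent. With zero events the upper limit is 1 − 0.025^(1/n).

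| PTFs | Injections | Rate | 95% limits |
|---|---|---|---|
| 0 | 684 (all) | 0% | 0 to 0.54% |
| 0 | 570 (later doses) | 0% | 0 to 0.65% |
| 3 | 684 (all) | 0.44% | 0.09% to 1.28% |
| 3, all in later doses | 570 (later doses) | 0.53% | 0.11% to 1.53% |

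**Step 4: dose groups.** The documents give no group sizes, so these are illustrative assumptions. A group with half of the 684 injections (342) and no PTF has an upper limit of 1 − 0.025^(1/342) = 1.07%. A group with about a tenth (68) and no PTF has 1 − 0.025^(1/68) = 5.28%. The same count of zero carries about five times less information in the smaller group.

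**Step 5: the most that pooling could dilute a rate.** If no PTF ever occurred on site, the all-injection rate would be 570/684 = 5/6 of the later-dose rate. For example, a later-dose rate of 1.0% would appear as 0.83%. If technical faults are equally frequent in both settings, the dilution is zero.

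**The case against.** The case against has several parts.

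**The sub-study is descriptive and single-arm.** It has no success threshold and no planned comparison between doses. That is so, and no formal conclusion would be reversed. It does not remove the need for a denominator, because describing a failure frequency is the purpose of the exercise.

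**Denominators are partly available.** Doses administered enter the compliance calculation (Appendix R 11.4.1), and the percentage of patients with PTFs is secondary. Both are true, so a reader might construct a rate. But the compliance figure counts doses administered, not syringes attempted, and neither item is the primary analysis or carries an interval.

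**Injections cluster within patients.** An exact interval treats up to six injections from one patient as independent. This stands, and the fix has to allow for it.

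**The stronger reading.** A reader might infer that including the supervised first dose biases the primary result downwards by about 17%, and that 680 overstates the evidence on unsupervised use. The documents do not support this:
- A PTF needs a validated technical cause, and use-related events are classified as FDDs. Nothing indicates that technical faults are rarer on site.
- The rationale includes professional users, and the formal objective does not mention unsupervised use.
- Supervision of the first real dose is an inference from the site setting. The text requires observation only of the practice injection into the training pad.
- The protocol presents 680 as injections for evaluating PTFs, not as home injections, and the figure is right.

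What remains is that the first and later doses are given in different settings and can be displayed separately at no real cost. This is likely to matter more for PTCs and FDDs than for PTFs.

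**Conclusion.** The point holds for the missing denominator and interval. The primary result as specified cannot express or bound the device failure rate, and its layout by dose groups of uncontrolled size makes the counts hard to interpret. On the plan's assumptions, a rate with an interval would bound the failure rate at 0.54% if no PTF occurred in 684 injections, or at 0.65% for the 570 later doses alone. Both limits assume independent injections, and the second treats every dose after the first as normally off-site.

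The point does not extend to a claim that pooling the first dose distorts the primary result. One sixth is the largest dilution on the planned numbers, reached only if no failure occurs on site, and it is not shown for technical failures. Severity is low: the sub-study is optional and descriptive, and the change is one of reporting.

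**What to change.** In Protocol Appendix R 11.4.2.1 and SAP Appendix K (Efficacy (Device) analysis):

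1. Report validated PTFs per PFS-S injection attempted, overall and by dose group, with the count, the number of injections and an exact two-sided 95% confidence interval. If more than a few PTFs occur, add an interval that allows for clustering within patient.
2. As a supportive display, show the first on-site (Visit 101) injection separately from later injections, for PTFs, PTCs and FDDs. Split by dose order: the listed diary questions ask whether the injector was the trained person, not who injected or where, so a split by injector or place is not shown to be derivable.
3. In Appendix R 11.1 and the matching SAP text, keep about 680 as the total and add that about 570 of these are later, normally off-site doses.

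**Cost.** Wording changes and a little more analysis. Diary feedback on each injection already goes into the e-CRF (Appendix R 10.1.2), so the first-versus-later split needs no new data field. The later-dose subset has a slightly wider interval, with a zero-event upper limit of 0.65% instead of 0.54%.

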##### **11.4.2.2 Analyses of secondary and exploratory endpoints**

Descriptive statistics will be used for continuous variables; discrete variables will be described using counts and proportions. Data will be presented by treatment dose group.

Serum concentrations of functional sarilumab will be summarized using standard descriptive statistics such as arithmetic and geometric means, standard deviation (SD), standard error of the mean (SEM), coefficient of variation (CV%), minimum, median, and maximum by visit

For PK parameters  $C_{\text{trough}}$ , estimates and 90% CIs for the ratio of geometric means (Day 85 versus Day 1) will be provided using a linear fixed effects model on the log-transformed data. Serum trough concentrations of functional sarilumab will be evaluated in patients on stable dose of sarilumab at V101 (D1) before using the PFS-S. Patients are considered to be on stable dose of sarilumab at V101 (D1) if they receive the same dose of sarilumab without treatment interruption for at least 24 weeks in LTS11210 prior to V101. Patients changing dose during the 12 week sub-study will be excluded from the  $C_{\text{trough}}$  analyses.

##### **11.4.2.3 Multiplicity considerations**

[figure not shown]
Not applicable

## **11.5 INTERIM ANALYSIS**

No interim analysis is planned.

## 12 HANDLING PROCESS FOR PRODUCT TECHNICAL COMPLAINT REPORTING

PFS-S = pre-filled syringe with safety system; PTC= product technical complaint; PTF = product technical failure; FDD = failed drug delivery

# LTS11210 Amended Protocol 9

## LIST OF ABBREVIATIONS AND DEFINITION OF TERMS

ACR	American College of Rheumatology
ADA	anti-drug antibody
AE(s)	adverse event(s)
AESI	adverse events of special interest
ALP	alkaline phosphatase
ALT	alanine aminotransferase
ANA	antinuclear antibody
ANC	absolute neutrophil count
AST	aspartate aminotransferase
ATC	Anatomic Therapeutic Class
BMI	body mass index
BUN	blood urea nitrogen
CAC	Cardiovascular adjudication committee
CCP	cyclic citrullinated peptides
CI	Confidence interval
CLcr	creatinine clearance
CPK	creatine phosphokinase
CRP	C-reactive protein
CRF	case report form
CSR	clinical study report
CV	coefficient of variation
CV event	cardiovascular event
DAS28	Disease Activity Score 28
DBP	diastolic blood pressure
DILI	drug induced liver injury
DMARD	disease modifying antirheumatic drug
DNA	deoxyribonucleic acid
ds-DNA	double-stranded DNA
ECG	electrocardiogram
EULAR	European League Against Rheumatism
HAQ-DI	Health Assessment Questionnaire-Disability Index
HbA1c	hemoglobin A1C
HDL	high density lipoprotein
HLGT	high level group term
HLT	high level term
HR	heart rate
hs-CRP	high sensitivity C-reactive protein
IL6-R	interleukin 6 receptor
IMP	investigational medicinal product
ITT	intent to treat

IVRS	Interactive Voice Response Systems
LDH	lactate dehydrogenase
LDL	low density lipoprotein
LLN	lower limit normal
LLT	lower level term
MACE	major adverse cardiovascular event
MedDRA	Medical Dictionary for Regulatory Activities
MTX	Methotrexate
PCSA	potentially clinically significant abnormalities
PFS-S	pre-filled syringe with safety system
PK	pharmacokinetic
PT	preferred term
PTC	product technical complaint
PTF	product technical failure
q2w	bi-weekly (every-other-week)
RA	rheumatoid arthritis
RBC	red blood cell
SAE	serious adverse event
SAP	statistical analysis plan
SBP	systolic blood pressure
SD	standard deviation
SF-36 V2	Short Form 36 Version 2
SJC	swollen joint count
SMQ	standardized MedDRA query
SOC	system organ class
TEAE	treatment emergent adverse event
TJC	tender joint count
TNF	tumor necrosis factor
ULN	upper limit normal
VAS	Visual Analogue Scale
WBC	white blood cell
WHO-DD	World Health Organization – Drug Dictionary
WPAI	Work Productivity and Activity Impairment

## 1 OVERVIEW AND INVESTIGATIONAL PLAN

This document is the statistical analysis plan (SAP) for the final clinical study report (CSR) and guidance for interim analysis reports during the study.

### 1.1 STUDY DESIGN AND RANDOMIZATION

This is a multicenter, multinational open label long term study, for patients with RA who participated and completed EFC11072, ACT11575, EFC10832, SFY13370, and EFC13752 or for patients from 12 weeks onward with per protocol defined lack of efficacy from EFC10832. Patients, who were randomized in Part B of EFC11072 in a treatment arm subsequently not retained following pivotal dose selection, were also eligible for enrollment.

The 5 previous studies are described briefly below:

**EFC11072:** A randomized, double-blind, placebo-controlled, multi-centre, two-part, dose ranging (Part A) and confirmatory (Part B) study with an operationally seamless design, evaluating efficacy and safety of sarilumab added to methotrexate (MTX) in patients with active rheumatoid arthritis who are inadequate responders to MTX therapy. The study was completed. In the dose ranging part of the study (Part A), 5 doses (100 mg weekly [qw], 150 mg qw, 100 mg every other week [q2w], 150 mg q2w, and 200 mg q2w) and placebo were tested in combination with methotrexate (MTX). The confirmatory (Phase 3) portion (Part B) which initially had the same 6 arms (Cohort 1) and then after Phase 3 dose selection (150 mg q2w and 200 mg q2w) had 3 arms (Cohort 2: placebo, 150 mg q2w, 200 mg q2w) for 52-week treatment. In EFC11072 Part B, beginning at Week 16, patients with lack of efficacy (defined as less than 20% improvement from baseline on 2 consecutive visits in either TJC or SJC, or with any other clear lack of efficacy based on Investigator judgment) might have started OL rescue therapy with sarilumab 150 mg qw (150 mg qw prior to Phase 3 dose selection; 200 mg q2w after Phase 3 dose selection) in this study. These patients were also eligible to enter LTS11210 study if completed the treatment period. There were 1283 patients who rolled over to LTS11210.

**ACT11575:** A randomized, double-blind, parallel-group, placebo- and active calibrator-controlled study assessing the clinical benefit of sarilumab on top of MTX in patients with active RA who have failed previous TNF- $\alpha$  antagonists was terminated by the Sponsor due to administrative reasons with only 16 patients enrolled. There were 7 patients who rolled over to LTS11210.

**EFC10832:** A randomized, double-blind, parallel-group, placebo-controlled study assessing the efficacy and safety of sarilumab added to DMARD therapy in patients with active rheumatoid arthritis (RA) who are inadequate responders or intolerant to tumor necrosis factor-alpha (TNF- $\alpha$ ) antagonists. Patients are randomized into 3 arms (placebo, 150 mg q2w, 200 mg q2w) with 24-week treatment. There were 456 patients who rolled over to LTS11210.

**SFY13370:** A randomized, double-blind, double-dummy study assessing the safety and tolerability of sarilumab and tocilizumab in patients with rheumatoid arthritis who are inadequate responders to or intolerant of TNF antagonists. Patients are randomized into 3 arms (Tocilizumab IV 4/8 mg/kg q4w, 150 mg q2w, 200 mg q2w) with 24-week treatment. There were 168 patients who rolled over to LTS11210.

**EFC13752:** An Open-label, Randomized, Parallel Group Study Assessing the Immunogenicity and Safety of Sarilumab Administered as Monotherapy in Patients with Active Rheumatoid Arthritis. Patients are randomized into 2 arms (150 mg q2w, 200 mg q2w) with 24-week treatment. There were 111 patients who rolled over to LTS11210.

Patients may have been exposed with sarilumab for 12 weeks if they were initially randomized in EFC11072 Part A or ACT11575; between 2 and 52 weeks, if initially randomized in EFC11072 Part B; between 12 and 24 weeks, if initially randomized in EFC10832; or for 24 weeks, if initially randomized in SFY13370 and EFC13752.

Initially in LTS11210, patients received 150 mg of sarilumab SC weekly as the highest dose studied in EFC11072 Part A. The reduced dose (due to neutropenia, thrombocytopenia, or an increase in liver enzymes [ALT]), was 150 mg q2w. Once the dose regimens were selected for the Phase 3 studies (150 mg q2w and 200 mg q2w), patients already ongoing in the study at the highest dose were switched to the new highest sarilumab dose 200 mg q2w, as soon as permitted by administrative process. Patients previously assigned to the reduced dose of 150 mg q2w due to safety issue continued to receive 150 mg q2w.

The duration of the treatment period in the study will be at least 264 weeks, or up to a maximum of 516 weeks (*except in the UK where the duration of treatment will be 264 weeks*) described in Protocol Amendment 9. However, some patients may complete this study with 260 week treatment duration per Protocol Amendment 8 before the approval of Protocol Amendment 9 in their countries. The total maximum duration of study participation for a patient may be up to 523 weeks.

- 1-week screening period if applicable
- 516-week maximum treatment period in LTS11210 (for the earliest patients enrolled in LTS11210 in 2010 if sarilumab is not commercialized by 2020)
- 6-week follow up period as required per protocol

Patients will either enter a 1-week screening period after the EOT visit (Visit 1 in LTS11210) in initial studies (for patients from EFC11072 Part A or Part B1 and ACT11575), or enrol directly into the treatment period (for patients from EFC11072 Part B2, EFC10832, SFY13370, or EFC13752, the EOT visit in the initial study corresponds to the randomization visit, Visit 1/2 in LTS11210).

At Visit 2 or Visit 1/2 (Week 0) after confirmation of eligibility, patients will be administered the first open-label dose of sarilumab at the investigational site and will be observed for 30 minutes for any medical events. At dosing time points occurring outside site visits, sarilumab can be injected by the patients, or by trained caregivers.

Patients will return for the safety follow-up visit 6 weeks after the EOT visit (V49). In case of early treatment discontinuation, patients are required to complete the EOT visit (V49) and to return for the 6-week safety follow-up visit (Visit 50) as well.

The study will be considered completed for a patient at the time he/she completes all the scheduled procedures.

An optional 12-week sub-study aiming to evaluate the usability of pre-filled syringe with safety system (PFS-S) will be conducted in some countries. Patients enrolled in LTS11210 at selected sites in those countries may participate in the PFS-S sub-study from Week 24 of the main study after providing written informed consent for the sub-study. However, patients may continue to participate in the main trial without participating in the PFS-S sub-study if they wish. Full details of the PFS-S sub-study are presented in [Appendix K](#).

